For subjects with NHL, archival tissue from the most recent available biopsy or surgery or fresh tumor tissue (preferred) or archival tissue from the most recent available biopsy or surgery (within 4 months prior to the start of screening) must be obtained pretreatment. For subjects undergoing a biopsy, adequate tumor tissue should be acquired via excisional biopsy, incisional biopsy or core needle biopsy (e.g., > 3 passes using a 16-gauge core needle). Confirmation of tumor in biopsy with fine needle aspirate, touch prep, or FFPE processing is requested when possible. The tumor lesion selected should not have been previously irradiated and should not be an index lesion that is followed for response assessment. Alternatively, cells from a bone marrow aspirate may be obtained in subjects with bone marrow involvement due to NHL (>50% NHL cells). For subjects undergoing a biopsy, adequate tumor tissue should be acquired via excisional biopsy, incisional biopsy or core needle biopsy (e.g., ≥ 3 passes using a 16 gauge core needle). Tissue will be submitted for evaluation of the percentage of tumor cells and analysis of genetic alterations and/or gene expression that may predict anti-lymphoma activity and/or pharmacodynamics activity. In addition, tumor may be evaluated for known prognostic characteristics (e.g., for DLBCL: ABC or GCB subtype; expression of BCL2, BCL6, Ki-67, CD20, and MYC; other mutational status), for PDL1 status, and for immune infiltration.

Comprehensive information on tissue acquisition, handling, storage and sample shipments can be found in the laboratory manual "Procedures for Processing and Shipping PK and Biomarker Samples." biomarker sample process documents.

Section 14.1.2. Stage 2 (Cohort Expansion)

Changes: A statistical justification for accrual of additional patients with FL to receive LAM-002A monotherapy or LAM-002A/rituximab was included.

As indicated in Section 6.1.2, expansion cohorts of 6 subjects will be accrued. Enrollment of 6 subjects per cohort offers the opportunity to determine if there is any antitumor activity sufficient to warrant further development in the selected tumor types. An ORR of \geq 35% is considered of potential interest in each of the selected indications. If 0/6 subjects in a cohort

Clinical Study Report 16.1 Study Information Protocol: LAM-002A-NHL-CLN01

Version 9, 18 Feb 2020

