experience an objective response, then a population ORR of \geq 35% for that cancer can be excluded with > 90% certainty (1-sided exact binomial 90% CI upper bound = 32%).

Based on the observation of objective responses among study subjects with FL receiving either LAM-002A monotherapy or LAM-002A/rituximab, expanded accrual of subjects with relapsed FL is planned to evaluate the level of activity with these 2 regimens. Preference will be given to enrolling subjects to receive LAM-002A monotherapy before enrolling subjects to receive LAM-002A/rituximab.

Based on historical data with other treatments (Zelenetz 2014), it is known that an ORR of \leq 20% in subjects with relapsed FL receiving LAM-002A monotherapy would be uninteresting while achieving a target ORR of \geq 40% would suggest that further development is warranted. Sequential boundaries will be used to continuously monitor that the ORR is \geq 40% while excluding an ORR of \leq 20% using a 1-sided test with a significance level of 0.05. A significant result with this testing would conclude with 95% confidence that the actual ORR is \geq 20%. Accrual of up to \sim 20 evaluable subjects will be considered with the potential to stop accrual early if the boundary is crossed. Thus, accrual can be considered sufficient if the following n/N values are observed: 4/5, 4/6, 4/7, 5/8, 5/9, 5/10, 5/11, 6/11, 6/12, 6/13, 6/14, 7/15, 7/16, 7/17, 8/18, 8/19, 8/20. For all these values, the ORR is \geq 40% with a lower 1-sided binomial confidence bound of \geq 20%.

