Changes: Text was included to explain the addition of an extension stage to the study.

The extension stage (Stage 3) can begin once the last study subject has completed at least 8 cycles of study treatment. At this time, the study sponsor will conclude the dose-escalation and expansion stages of the study, will collate and verify all study data through an appropriate data cutoff date, and will lock the study database for preparation of a study report. Subjects who are still safely benefiting from Stage 1 or Stage 2 study therapy as of the data cutoff date may electively continue their current regimen of study therapy in Stage 3, receiving clinical care and diagnostic testing consistent with conventional practice standards as deemed appropriate by the treating investigator. Therapy in Stage 3 may continue in the absence of protocol-defined reasons to discontinue therapy. During Stage 3, collection of clinical data by the sponsor will be limited to serious adverse event (SAE) reports. Study drug accountability will be managed per site procedures; relevant pharmacy records may be collected by the sponsor to document study drug disposition.

Section 6.2. Number of Subjects

Changes: Text was included consistent with addition of an extension stage to the study.

As many as 145 subjects will be enrolled, assuming that:

- In the dose-escalation stage of the study, the total number of subjects will depend upon the numbers of subjects accrued to each dose level and the number of dose levels evaluated. If 6 subjects are enrolled at all open starting dose levels (Dose Levels 5, 6, 7, and 8) and 6 additional subjects are enrolled at the MTD or RD, as many as 30 subjects could be enrolled. To allow for the possibility that some subjects may not be fully evaluable for DLT or that an intermediate dose level might be evaluated, up to ~45 subjects may be enrolled.
- In the expansion stage of the study, if all 8 potential expansion cohorts are accrued, as many as ~76 subjects could be enrolled. To allow for the possibility that some subjects may not be fully evaluable for efficacy or to establish bounds on efficacy estimates with greater confidence, up to ~100 subjects may be enrolled.

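### The FL response boundaries in Section 14.1.2 do not deliver the stated one-sided 0.05 level: checked at every N, their type I error is 8.7% (monotherapy) and 9.9% (combination), before any effect of choosing FL after responses were seen

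*Combined protocol and SAP*

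**What the plan says.** The text was inserted into Section 14.1.2 (Stage 2, Cohort Expansion) by the amendment that enlarged the FL cohorts.

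- **Starting point.** Before the change, "expansion cohorts of 6 subjects will be accrued".
- **Reason for enlarging.** More FL accrual is planned "Based on the observation of objective responses among study subjects with FL receiving either LAM-002A monotherapy or LAM-002A/rituximab".
- **Monotherapy rule.** ORR of 20% or less is uninteresting and 40% or more is the target. The test is one-sided at 0.05, monitored continuously to about 20 evaluable subjects. Accrual is sufficient at 4/5, 4/6, 4/7, 5/8, 5/9, 5/10, 5/11, 6/11, 6/12, 6/13, 6/14, 7/15, 7/16, 7/17, 8/18, 8/19 or 8/20.
- **Combination rule.** It excludes 39% and targets 60%, again one-sided at 0.05, with values 7/10, 8/11, 8/12, 9/13, 9/14, 10/15, 10/16, 11/17, 11/18, 12/19 and 12/20.
- **Claim.** "A significant result with this testing would conclude with 95% confidence that the actual ORR is" at least 20%. A parallel sentence gives 39% for the combination. The section adds that every listed value has a one-sided lower bound of at least 20% (or 39%).
- **Numbers.** Section 6.1.2, Table 2, replaces 6 by up to about 20 in cohorts 1 and 5. Section 6.2 says that "if all 8 potential expansion cohorts are accrued, as many as ~76 subjects could be enrolled".

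**The concern.** A lower bound that is valid for one look at a fixed N loses its level when it is checked after each subject and the first favourable result ends accrual. The inserted text describes continuous monitoring but shows no adjustment for it. A second issue sits on top: FL was singled out because responses had been seen, the boundary was written afterwards, and the numbers suggest that the same subjects are counted again.

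The plan ties these rules to whether further development is warranted. An overstated confidence therefore bears on that decision and on how the FL response rate will be read.

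**Working it through.** **1. Reproducing the plan's figures, one look at a time.** For each n/N, take the one-sided 95% Clopper-Pearson lower bound and the tail P(X ≥ n | N, p0).

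- 8/20 at p0 = 0.20: bound 21.7%, tail 0.032.
- 12/20 at p0 = 0.39: bound 39.4%, tail 0.047.
- All combination values have bounds of at least 39%.
- All monotherapy values have bounds of at least 20%, except 5/11: bound 19.96%, tail 0.0504. N = 11 appears twice in the list, as 5/11 and 6/11.

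Apart from 5/11, the lists are pointwise 95% bounds.

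**2. Type I error of the whole rule.** Let a_N(k) be the probability of k responders after N subjects without an earlier crossing, and b_N the listed value. Then

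a_N(k) = a_{N−1}(k)(1 − p0) + a_{N−1}(k − 1)p0.

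The crossing probability at N is the sum of a_N(k) over k ≥ b_N. Those paths are removed before the next subject.

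- *Monotherapy, p0 = 0.20.* First crossings: 0.0067 (N=5), 0.0102 (6), 0.0164 (7), 0.0046 (9), 0.0095 (10), 0.0147 (11), 0.0040 (13), 0.0081 (14), 0.0025 (16), 0.0053 (17), 0.0017 (19), 0.0036 (20). The sum is **0.087**. It passes 0.05 at N = 11. Using 6/11 instead of 5/11 gives 0.081.
- *Combination, p0 = 0.39.* First crossings: 0.0477 (10), 0.0156 (12), 0.0118 (14), 0.0095 (16), 0.0078 (18), 0.0065 (20). The sum is **0.099**. It passes 0.05 at N = 12. At p0 = 0.40 the error is 0.114.

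The confidence is therefore 1 − 0.087 ≈ 91% and 1 − 0.099 ≈ 90%. Power of the listed rules is 69% at ORR 40% and 68% at ORR 60%.

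**3. Are earlier FL subjects counted?** Two cohorts of 20 and six of 6 give 20 + 20 + 36 = 76, the total in Section 6.2. If the 20 were additional to 6, the total would be 26 + 26 + 36 = 88. Counting them is the natural reading, but it is an inference.

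**4. Error given the responses already seen.** Assume six earlier subjects, all counted. Let R(k) be the probability of crossing by N = 20 starting from k/6. Then

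error given at least m responses = Σ_{k≥m} Bin(k; 6, p0) R(k) / Σ_{k≥m} Bin(k; 6, p0).

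Monotherapy weights for k = 1, 2, 3 and ≥4 are 0.3932, 0.2458, 0.0819 and 0.0170. The R(k) values are 0.0236, 0.1071, 0.4111 and 1.

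| Responses in first 6 | Monotherapy | Combination |
|---|---|---|
| at least 1 | 0.0862/0.7379 = 11.7% | 0.0990/0.9485 = 10.4% |
| at least 2 | 0.0770/0.3446 = 22.3% | 0.0981/0.7508 = 13.1% |
| at least 3 | 0.0506/0.0989 = 51.2% | 0.0905/0.4350 = 20.8% |
| exactly 1 | 2.4% | 0.4% |
| exactly 2 | 10.7% | 2.4% |
| exactly 3 | 41.1% | 10.1% |

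The numerators for at least 1 response are the unconditional errors when expansion requires at least one response: 8.6% and 9.9%, no higher than in step 2.

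**5. Do simpler repairs work?** Dropping the monotherapy points at N = 5 and 6 leaves the error at 8.7%, because four responders by then also meet 4/7. Applying the listed boundary to 14 new subjects only gives 7.4% and 7.5%.

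**The case against.** A reader might infer that re-use of the triggering responders is established and is what breaks the 95% claim. The documents do not support that.

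- **No passage says the earlier subjects count.** The totals are approximate, and Section 6.2 allows up to about 100. Stage 1 also admitted FL, so some responders may lie outside n/N. Cohort 5 previously took FL or marginal zone lymphoma, so six earlier FL subjects is an assumption there.
- **Continuing after early responses and keeping those subjects is ordinary two-stage practice.** It does not raise the unconditional error (step 4).
- **The conditional figures depend on an unknown count.** With exactly one response they are below 5%. The 51% also includes cases with 4/6 or more, where the rule was already met; without them the monotherapy figures are 9.6%, 18% and 41%. With one final test at N = 20 and a trigger of at least one response, the error would be 4.3% and 4.9%.

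All of this stands, and it limits the selection argument to a range. It does not touch step 2, which needs no selection.

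Two further points have some force. This is a Phase 1 accrual rule, not a confirmatory test; but the plan itself attaches a significance level and a confidence to it. The text is the wording inserted by an amendment, and the body of Section 14.1.2 is not in the part available, so an adjustment stated there cannot be ruled out.

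**Conclusion.** The 0.05 level and the 95% confidence do not hold for the rules as listed. The certain cause is the use of unadjusted pointwise bounds at every N: the error is 8.7% at ORR 20% and 9.9% at ORR 39%. This rests only on the listed values, a look at each listed N, and stopping at the first crossing. The statement that every listed monotherapy value has a bound of at least 20% also fails narrowly, at 5/11.

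Re-use of the responders that prompted the expansion is a probable second problem of unknown size. If six earlier subjects are counted, the conditional error runs from below 5% (exactly one response) to 51% (monotherapy) or 21% (combination) given at least three.

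**What to change.** 1. In both the monotherapy and combination paragraphs of Section 14.1.2, delete the 0.05 and 95% statements for the continuously monitored count, or restate them as about 91% and 90% before any selection effect. Alternatively, use a boundary with overall one-sided error of 0.05. For example, a pointwise level of 0.025 gives 4.9% (9/20 at the end, power 58%) and 4.0% (13/20 at the end, power 50%), also before selection. Resolve the double entry at N = 11.
2. State whether FL subjects enrolled before the amendment count in n/N.
3. Report the pooled ORR as descriptive, and subjects enrolled after the amendment separately with an exact confidence interval. If accrual stopped on the pooled count, that separate estimate is not strictly unbiased, and the report should say so.
4. If a 95% statement is wanted, base it on one exact test in a fixed number of new subjects. With 14, at least 6/14 has alpha 4.4% and power 51% at ORR 40%; at least 9/14 has alpha 4.97% and power 49% at ORR 60%. Removing the points at N ≤ 6 is not a substitute.

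The cost is a wording change and one extra analysis, with no extra subjects. The downsides are a less favourable stated confidence, a wider interval in about 14 subjects, and lower power than the 69% and 68% of the listed rules.

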As noted above, the target ORR with LAM-002A alone is ~40%. Adding rituximab or rituximab hyaluronidase human to LAM-002A would be expected to enhance the ORR over that associated with single-agent LAM-002A. Thus, the combination of LAM-002A/rituximab could warrant further development if an ORR of \geq 60% could be targeted in preference to an ORR of < 40%. Accordingly, for combination therapy, sequential boundaries will be used to continuously monitor that the ORR is \geq 60% while excluding an ORR of 39% using a 1-sided test with a significance level of 0.05. A significant result with this testing would conclude with 95% confidence that the actual ORR is \geq 39%. Accrual of up to \sim 20 evaluable subjects will be considered with the potential to stop accrual early if the boundary is crossed. Thus, accrual can be considered sufficient if the following n/N values are observed: 7/10, 8/11, 8/12, 9/13, 9/14, 10/15, 10/16, 11/17, 11/18, 12/19, 12/20. For all these values, the ORR is \geq 60% with a lower 1-sided binomial confidence bound of \geq 39%.

Experience indicates the rates of discontinuations from rituximab or atezolizumab therapy are < 5% (Genentech 2016, Genentech 2017). A rate of AE discontinuations of therapy due to adverse events of \geq 25% in the 2 combination therapy groups of LAM-002A/rituximab (N = 12) or LAM-002A/atezolizumab (N = 12) would suggest a potential adverse interaction among the components of the combination therapy. Sequential Pocock-type boundaries will be used to continuously monitor the rate of AE discontinuations and to test the null hypothesis, after each subject, that the event rate is \geq 0.25 using a 1-sided significance test of \sim 0.05. AE discontinuation rates will be considered excessive if the following n/N values are observed: -/1, -/2, 3/3, 3/4, 4/5, 4/6, 5/7, 5/8, 5/9, 6/10, 6/11, 7/12. With this method, the probability of detecting an AE discontinuation safety signal ranges from 0.091 to \geq 0.820 for true discontinuation rates of 25% to \geq 60%. If excessive levels of AE discontinuation are observed, the sponsor, working in collaboration with the cooperating companies and investigators, will take appropriate actions (eg, continuation of the cohort with modifications in design or monitoring plan, interruption of cohort accrual, cohort therapy discontinuation).

Version 9, 18 Feb 2020

Section 22. List of References

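### The FL response-rate boundaries repeat an unadjusted 5% test after every subject: true one-sided error is 8–10%, not 5%, and the entry 5/11 misses its own bound

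*Combined protocol and SAP*

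**What the plan says.** The text is in Section 14.1.2, Stage 2 (Cohort Expansion), as printed in the change summary for the amendment that enlarged the FL cohorts.

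- **Monotherapy.** An ORR of 20% or less is uninteresting, and a target of at least "40% would suggest that further development is warranted". The rule is: "Sequential boundaries will be used to continuously monitor that the ORR is" at least 40%, while excluding an ORR of at most "20% using a 1-sided test with a significance level of 0.05". Accrual runs to about 20 "evaluable subjects will be considered with the potential to stop accrual early if the boundary is crossed".
- **Monotherapy list.** "4/5, 4/6, 4/7, 5/8, 5/9, 5/10, 5/11, 6/11, 6/12, 6/13, 6/14, 7/15, 7/16, 7/17, 8/18, 8/19, 8/20". Every value is said to have a one-sided lower binomial bound of at least 20%.
- **Conclusion drawn from a crossing.** "A significant result with this testing would conclude with 95% confidence that the actual ORR is" at least 20%.
- **Combination with rituximab.** The construction is the same, with a target of 60%, 39% to be excluded and a one-sided level of 0.05. The list is "7/10, 8/11, 8/12, 9/13, 9/14, 10/15, 10/16, 11/17, 11/18, 12/19, 12/20", and every value is said to have a lower bound of at least 39%.

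Neither ORR rule gives an adjusted per-look level, an error-spending scheme or the overall probability of crossing under the null. The AE-discontinuation rule in the same section is called Pocock-type and does report its crossing probability at the 25% null, 0.091.

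**The concern.** A 5% test has a 5% error rate if it is done once. If it is repeated after each subject and any crossing may end accrual, the error accumulates over looks. The lists look like single-look tests placed side by side, yet the text attaches the single-look level and confidence to the whole monitored procedure. The monotherapy list also gives two thresholds at one sample size ("5/10, 5/11, 6/11, 6/12"), so the rule at N=11 is ambiguous.

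These lists determine when FL accrual is enough, and the section ties the ORR targets to further development. If the error rate is understated, a crossing will be read as stronger evidence than it is. An ORR quoted after an early crossing will also tend to be too high.

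**Working it through.** **Inputs** (all from Section 14.1.2): null ORR 20% and target 40% (monotherapy); null 39% and target 60% (combination); one-sided 0.05; the two n/N lists; looks after every subject from N=5 to 20 and from N=10 to 20.

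**Step 1. Method check on the plan's own figure.** Let f(N,k) be the probability of having k responses at N without having crossed earlier:

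f(N,k) = f(N−1,k)(1−p) + f(N−1,k−1)p,

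with every k at or above the boundary removed at each look and added to the crossing probability. Applied to the AE-discontinuation list, this gives 0.0908 at 25% and 0.8201 at 60%. The plan states 0.091 and 0.820, so the method matches.

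**Step 2. What each entry is.** The single-look p-value is P(X ≥ n) with X ~ Binomial(N, null ORR).

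- 4/5 at 20%: 5(0.2⁴)(0.8) + 0.2⁵ = 0.0067.
- 8/20 at 20%: 0.0321; one response fewer, 7/20, gives 0.0867.
- 12/20 at 39%: 0.0466; 11/20 gives 0.1090.

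Leaving 5/11 aside, the single-look p-values run from 0.0067 to 0.0439 (monotherapy) and from 0.0249 to 0.0497 (combination). In every case one response fewer gives a p-value above 0.05. The lists are therefore unadjusted fixed-sample 5% tests.

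**Step 3. The entry 5/11.** P(X ≥ 5 | N=11, 20%) = 0.0504, and the exact (Clopper–Pearson) 95% lower bound is 19.96%. The other 16 monotherapy entries have bounds of 20.6% to 34.3%. All 11 combination entries have bounds of 39.0% to 43.6%.

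**Step 4. Overall error of the monitored rule.** Probability of first crossing at each look, under the null; looks not shown contribute zero.

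| Rule | Contributions by N | Total |
|---|---|---|
| Monotherapy, 20%, as listed | 5: .0067; 6: .0102; 7: .0164; 9: .0046; 10: .0095; 11: .0147; 13: .0040; 14: .0081; 16: .0025; 17: .0053; 19: .0017; 20: .0036 | 0.0873 |
| Monotherapy, 20%, 6/11 only | 5: .0067; 6: .0102; 7: .0164; 9: .0046; 10: .0095; 12: .0029; 13: .0063; 14: .0100; 16: .0028; 17: .0058; 19: .0018; 20: .0038 | 0.0809 |
| Combination, 39% | 10: .0477; 12: .0156; 14: .0118; 16: .0095; 18: .0078; 20: .0065 | 0.0990 |

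Simulation with 400,000 paths gives 0.0874, 0.0810 and 0.0990. At a true ORR of 40% the combination rule crosses with probability 0.1144. The cumulative error passes 0.05 at N=11 (monotherapy as listed), N=12 (6/11 only) and N=12 (combination).

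**Step 5. Sensitivity to the looks.** Starting at N=6 or N=7 leaves the monotherapy total unchanged. Starting at N=12 gives 0.061 for monotherapy and 0.089 for the combination. Only a single analysis at N=20 stays below 0.05 (0.0321 and 0.0466).

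**Step 6. Lower bounds that respect the stopping rule.** Under stagewise ordering, the 95% lower bound is the ORR at which the probability of crossing at or before the observed look equals 0.05.

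| Result | Single-look bound | Stagewise bound |
|---|---|---|
| 8/20, monotherapy, 6/11 only | 21.7% | 17.7% |
| 8/20, monotherapy, as listed | 21.7% | 17.3% |
| 12/20, combination | 39.4% | 34.8% |

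**Step 7. Size of the estimation bias (monotherapy as listed).** Among cohorts that cross, the mean observed ORR is 53% when the truth is 20% and 55% when it is 40%. Part of this is ordinary selection on success: a fixed N=20 design restricted to results of at least 8/20 gives 42% and 47%. Averaged over all cohorts, crossing or not, the listed rule gives 21.6% and 46.8%.

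**The case against.** The strongest reply is about context. This is an open-label Phase 1 expansion seeking preliminary activity. Stopping at a crossing is optional, and no crossing by itself commits the sponsor to an efficacy claim. If accrual always ran to 20 and only the final count were tested, the error would be 3.2% and 4.7%. That is correct, but it describes a different procedure from the continuous monitoring with early stopping to which the section attaches its level and confidence. The Phase 1 setting is a reason to accept a higher error rate, not to state a lower one.

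Second, 5/11 misses by very little: 19.96% rounds to 20%, and the section prints bounds as whole percentages elsewhere. It is probably a stray entry. It still fails the exact criterion that the other entries meet, shares N=11 with a different threshold, and raises the overall error by 0.6 percentage points.

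Third, the main body of Section 14.1.2 and the efficacy-analysis section are in the part of the document not available here, so an adjustment described only there cannot be excluded. The later changes that are available leave these boundaries alone, so they are presumed current.

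Fourth, the means among crossing cohorts overstate the bias caused by sequential looks unless set beside the comparators in Step 7. That stands, and they should be read together.

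**Conclusion.** The concern holds. Both FL boundaries are single-look 5% tests repeated without adjustment. Under the monitoring described, the one-sided error is 8.7% for monotherapy as listed (8.1% with 6/11 only) and 9.9% for the combination, against the stated 5%. The confidence attached to a crossing is therefore about 91% (1 − 0.087) and 90% (1 − 0.099), not 95%. For a crossing at the final look, the valid 95% lower bound falls below the ORR the rule claims to exclude: 17.7% against 20% (6/11 only), and 34.8% against 39%. The entry 5/11 narrowly fails its stated bound and duplicates N=11.

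This assumes a look after every evaluable subject over the listed range, that any crossing counts as a significant result, independent responses with a common ORR, and that the amendment text is the current text.

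**What to change.** Delete 5/11 from the monotherapy list. Then take one of two routes.

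**(a) Keep the lists and correct the claims.** State the overall one-sided error of the monitored rule as 0.081 (monotherapy vs 20%) and 0.099 (combination vs 39%). Remove the 95% confidence statements. Report the ORR after a crossing with a stagewise-ordering lower bound. This changes wording only and leaves accrual and the chance of crossing at target (about 0.68 for each rule) as they are; the cost is a less favourable stated error. If monitoring actually used 5/11, the monotherapy error to report is 0.087.

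**(b) Replace the lists with ones whose exact overall error is below 0.05.**

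- Monotherapy: 4/5, 4/6, 5/7, 5/8, 5/9, 6/10, 6/11, 6/12, 7/13, 7/14, 7/15, 8/16, 8/17, 8/18, 8/19, 9/20 (error 0.049).
- Combination vs 39%: 8/10, 8/11, 9/12, 9/13, 10/14, 10/15, 11/16, 12/17, 12/18, 13/19, 13/20 (error 0.047; 0.056 if the true ORR is 40%).

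The chance of crossing at the target ORR falls from 0.68 to 0.58 for monotherapy and from 0.68 to 0.53 for the combination.

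Route (a) is the better fit if FL accrual is already complete, since new boundaries would then be set after the data were seen. The Version 9 text on closing Stages 1 and 2 suggests that this may be so.

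### FL expansion cohorts: if accrual stops at a boundary crossing, raw n/N overstates the ORR and the fixed-sample 95% bound is not met at the later crossings

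*Combined protocol and SAP*

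**What the plan says.** The text is in section 14.1.2, Stage 2 (Cohort Expansion), as inserted by the amendment that enlarged the two FL cohorts. The later amendment text in the part available does not alter it.

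- **Monotherapy.** An ORR of 20% or less "in subjects with relapsed FL receiving LAM-002A monotherapy would be uninteresting", while 40% or more "would suggest that further development is warranted". "Sequential boundaries will be used to continuously monitor that the ORR is" at target, excluding the uninteresting rate "using a 1-sided test with a significance level of 0.05". Up to about "20 evaluable subjects will be considered", "with the potential to stop accrual early if the boundary is crossed". The points listed are "4/5, 4/6, 4/7, 5/8, 5/9, 5/10, 5/11, 6/11, 6/12, 6/13, 6/14, 7/15, 7/16, 7/17, 8/18, 8/19, 8/20". The paragraph then says that at all of them the ORR is at least 40% and the one-sided binomial lower bound at least 20%, and that a significant result gives 95% confidence in the latter.
- **Rituximab combination.** The same construction, with 60% as target and 39% to exclude: "Thus, accrual can be considered sufficient if the following n/N values are observed: 7/10, 8/11, 8/12", and so on to 12/20.

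The analysis-set text (section 14.3.1) counts non-evaluable subjects as failures. No text in the part available names an estimate or interval adjusted for sequential stopping.

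**The concern.** A proportion read at a moment chosen because it is high tends to exceed the true rate, and a fixed-sample exact interval ignores the chances to cross at earlier looks. The paragraph applies both to data that may come from a stop-when-high rule, and the thresholds of 40% and 60% are its own criteria for further development. If the raw figures are carried into the report, the two FL cohorts will look more active, and more certainly so, than the design supports. This concerns the estimate and its bound, and it remains even if the boundary is accepted as an accrual guide.

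**Working it through.** **Inputs (section 14.1.2).** The listed boundaries, maximum 20, one-sided 0.05. Assumptions: a look after every evaluable subject from N=5 (monotherapy) or N=10 (combination), and a stop at the first crossing. Both 5/11 and 6/11 are listed; 6/11 is used unless stated. The true ORRs between and beyond the plan's reference rates are assumed.

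**1. The plan's own figures.** The lowest listed proportions are 8/20 = 40% and 12/20 = 60%. The fixed-N lower bound solves P(X ≥ n | N, p) = 0.05. For monotherapy it is at least 20.6% everywhere except 5/11 (19.96%; tail 0.0504 at 20%). For the combination its minimum is 39.0%, at 9/14. The stated figures therefore reproduce, as observed proportions and fixed-sample bounds.

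**2. Mean of n/N at the end of accrual.** E[n/N] = Σ (n/N) × (paths to that end point) × pⁿ(1−p)ᴺ⁻ⁿ, summed over first crossings and uncrossed ends at N=20.

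| Cohort, true ORR | P(cross) | Mean n/N | Mean n/N given a crossing |
|---|---|---|---|
| Mono, 20% | 0.081 | 21.5% | 53.8% |
| Mono, 30% | 0.336 | 34.4% | 53.4% |
| Mono, 40% | 0.679 | 46.8% | 55.5% |
| Combination, 50% | 0.355 | 52.7% | 68.5% |

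With 5/11 as the N=11 boundary the monotherapy means are 21.6%, 34.5% and 46.8%.

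Relaxing the assumptions at a true 40%:
- first look at N=7 (5/11 boundary): 45.4%
- four overrun subjects, capped at 20: 42.8%
- six overrun subjects: 41.8%
- always continuing to 20: 40.0%

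**3. Mean-unbiased estimate (UMVUE).** This is the share of paths to the stopping point whose first subject is a responder.
- 4/6: the path must be at 3/5, so C(4,2)/C(5,3) = 6/10 = 60.0%.
- 4/7: C(5,2)/C(6,3) = 10/20 = 50.0%.
- 5/9: the path must be at 3/7 and then have two responses, so C(6,2)/C(7,3) = 15/35 = 42.9%.
- 5/10: 36/91 = 39.6%.
- 8/20: 6360/21875 = 29.1% (with 5/11: 5912/20650 = 28.6%).

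**4. Stagewise lower bound.** Solve P(cross at or before stage N; p) = 0.05.

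| Crossing | Raw | UMVUE | Fixed-N bound | Stagewise bound |
|---|---|---|---|---|
| 5/10 | 50.0% | 39.6% | 22.2% | 20.3% |
| 6/12 | 50.0% | 36.6% | 24.5% | 19.95% |
| 6/13 | 46.2% | 34.9% | 22.4% | 19.3% |
| 6/14 | 42.9% | 33.2% | 20.6% | 18.5% |
| 8/20 | 40.0% | 29.1% | 21.7% | 17.7% |
| Comb. 7/10 | 70.0% | 70.0% | 39.3% | 39.3% |
| Comb. 8/12 | 66.7% | 60.0% | 39.1% | 37.4% |
| Comb. 12/20 | 60.0% | 50.4% | 39.4% | 34.8% |

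With 5/11 as the boundary, the stagewise bound is already 18.8% at 5/11 and is 17.3% at 8/20. As a check, the chance of ever crossing is 8.1% at a true 20% and 9.9% at a true 39%. Both exceed 5%, so the last-look bounds must lie below 20% and 39%.

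**The case against.** The best defence is that section 14.1.2 is a sample-size section. The list says when accrual is sufficient, and the statements of at least 40% and 60% are correct as observed proportions. A reader might infer that the plan commits to reporting n/N over evaluable subjects as the ORR. The documents do not go that far: section 14.3.1 uses all treated subjects, and the current efficacy analysis section (14.9) is not in the part available, so an adjusted estimate there cannot be ruled out. The 95% confidence wording, however, is an inferential claim and stands in 14.1.2 itself.

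Second, stopping is permitted, not required. First on-study imaging falls just before Cycle 3, and section 6.1.3 sets no restriction on the pace of monotherapy enrolment, so overrun is likely. That stands: 46.8% is the strict stop-at-first-crossing figure, not a forecast.

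Third, the choice of estimator matters. A stagewise one-sided median rule gives 38.0%, 36.0% and 34.7% at 6/14, 7/17 and 8/20, and a reader might attribute the whole shortfall from 40% to stopping. The same rule with no interim looks gives 39.5%, 38.5% and 37.7%, so much of that shortfall comes from the rule and the discreteness of the data. The UMVUE is free of this problem: at a fixed 20 it returns 40% for 8/20. The two methods agree on direction but not on size, so no single points-off correction can be quoted.

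**Conclusion.** The point holds in this form: conditional on stopping at the first crossing, raw n/N is biased upward, by 6.8 points on average at a true monotherapy rate of 40% (46.8 − 40) and 2.7 points at a true combination rate of 50% (52.7 − 50). The UMVUE is below 40% at monotherapy crossings from 5/10 on. The 95% statements fail from about 6/12 or 6/13 on (from 5/11 if that point is the boundary) and, in combination, from 8/12 on.

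The size depends on the look schedule and on actual stopping; overrun shrinks the bias, and always continuing to 20 removes it. A reader might also infer that the overstatement is greatest when the drug is inactive. That is so only among trials that cross: at a true 20% the mean given a crossing is 53.8%, but a crossing has probability 0.081 and the overall bias is 1.5 points.

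**What to change.** Keep the n/N lists as an accrual guide. In section 14.1.2 and the efficacy analysis:

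- State that the 40% and 60% figures are observed proportions only.
- Replace the fixed-sample bounds and the 95% confidence sentences with sequentially adjusted bounds, and say which N=11 boundary applies.
- If accrual stops at a crossing, report a pre-named adjusted estimate (for example the UMVUE) with its matching interval, computed at the stopping point.
- Beside it, show raw n/N for all treated subjects, including those enrolled after the crossing.

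Reporting both is preferable to replacing n/N outright: a stagewise estimate presumes that stopping is binding and does not itself absorb overrun subjects.

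The cost is a little more wording and programming, and a less favourable reported ORR, by an amount that depends on the crossing and the estimator. No extra subjects are needed.
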